[Part 2 of 2 of the document. The other parts are not shown.]

Considering anti-glycan autoantibodies recognizing Gd-IgA1 are implicated in the pathogenesis of IgA nephropathy, exposure to the GalNAc moiety of cemdisiran may pose a theoretical risk of stimulating the production of pathogenic autoantibodies and immune complexes in patients with IgA nephropathy. This could presumably occur when antidrug antibodies (ADAs) to cemdisiran's triantennary GalNAc (Tri-GalNAc) cross-react with Gd-IgA1. The risk of developing these cross-reactive antibodies is likely low. This is based on the low incidence of ADA to cemdisiran in study ALN-CC5-001 (see Section 1.2) and the distinct difference in structure of the O-GalNAc moieties on a Gd-IgA1 glycoprotein and the Tri-GalNAc moiety in cemdisiran. This low risk is further mitigated by excluding patients with confirmed pre-existing IgG/IgM/IgA ADAs to total drug and real time monitoring for development of de novo IgG/IgM/IgA ADAs after dosing with cemdisiran. Patients with confirmed de novo ADAs will be discontinued from study drug but will continue to be monitored until EOS visit and subsequent safety follow up. Patients who develop positive ADA will be followed until ADA titers return to baseline. Additional ADA samples will also be collected if any clinical evidence of progression of IgAN disease and/or relevant safety findings.

Detailed information about the known and expected benefits and risks of cemdisiran and additional information on the clinical and nonclinical data may be found in the current version of the IB.

Cumulatively, clinical data regarding the role of complement pathways in IgAN progression, robust nonclinical and clinical data with cemdisiran (see IB for more information), and prior and ongoing clinical experience with other RNAi therapeutics in humans suggest cemdisiran will have a favorable risk profile in the intended population and supports the initial clinical development of cemdisiran in IgAN. In addition, cemdisiran may address the unmet medical need for the first efficacious and disease-specific treatment for patients with IgAN.

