During the run-in period, patients will visit the study center 14, 8, and 2 weeks prior to randomization (Weeks 0, 6 and 12 of the run-in period). Patients will then return to the study center every 4 weeks after the start of study drug treatment period. The primary endpoint will be assessed at the end of treatment at Week 32.

At the end of treatment (Week 32), patients in the two treatment arms will enter the optional OLE period where they will receive cemdisiran at a dose of 600 mg every 4 weeks in combination with standard of care for 52 weeks. The first study drug administration of the OLE will be administered at Week 36. Patients will return to the study center at Week 40 and every 8 weeks thereafter during the OLE. Home visits, where locally feasible, may be arranged for cemdisiran administration in between 8-weekly study center visits (Weeks 44, 52, 60, 68 and 76), unless patients are required to visit the study center as judged necessary by the Investigator, or if home visits cannot be arranged. An end of treatment (EOT) visit will occur at Week 80 (OLE EOT) and an end of study (EOS) or early termination (ET) visit will be completed at Week 84 (OLE EOS/ET). For patients who complete the treatment period only who do not consent to continue to participate in the study in the OLE period, the EOS/ET visit will be at Week 36.

Patients will return to the clinical study center for safety follow-up visits approximately 13, 26, 39 and 52 weeks after the EOS/ET visit (regardless if EOS/ET visit is at Week 36 or Week 84), unless enrolled in another study with cemdisiran. Home visits, where locally feasible, may be arranged during safety follow-up at 13 and 39 weeks after the EOS/ET visit (regardless if EOS/ET visit is at Week 36 or Week 84).

Regular reviews of safety and tolerability data will be performed by an independent data monitoring committee (DMC) throughout the study with the primary purpose of protecting the safety of participating patients and the integrity of the study.

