## 6.7. Safety Assessments

The assessment of safety during the study will consist of the surveillance and recording of the frequency of AEs including SAEs, recording of concomitant medication and measurements of vital signs, weight and height, physical examination, and ECG findings and laboratory tests, including assessment of IgG/IgM/IgA ADA and CIC. Clinically significant abnormalities observed during the physical examination are recorded.

Safety will be monitored over the course of the study by a DMC as described in Section 3.7.

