#### **6.7.4.      Electrocardiogram**

Twelve-lead ECGs reporting rhythm, ventricular rate, RR interval, PR interval, QRS duration, and QT interval and Fridericia-corrected QT interval will be obtained, as specified in the Schedule of Assessments ([Table 1](#) and [Table 2](#)). Patients should be supine for at least 5 minutes before each ECG is obtained. A single 12-lead ECG will be performed at Screening. At all other time points, 12-lead ECGs will be performed in triplicate, with readings approximately 1 minute apart. 12-lead ECGs will be performed at predose; 60 minutes postdose; and 4 hours postdose in relation to the Day 1 and Week 32 cemdisiran or placebo doses.

When ECG and blood sample collection occur at the same time, ECGs should be performed before blood samples are drawn.

The Investigator or qualified designee will review all ECGs to assess whether the results have changed since the Baseline visit and to determine the clinical significance of the results. These assessments will be recorded on the eCRF. Additional ECGs may be collected at the discretion of the Investigator, or as per DMC advice.

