#### **6.7.5.1. Immunogenicity**

Blood samples will be collected to evaluate ADA and CIC. IgG/IgM/IgA ADA to total drug will be assessed at Screening and during the study. ADA samples will be tested in real time. Clinical study decision will be based on confirmed positive ADA results from the IgG/IgM/IgA assay. Confirmed positive ADA samples will be further characterized for cemdisiran domain specificity against the Tri-GalNAc component if a reliable method is established. Blood samples for ADA and CIC testing must be collected before study drug administration as specified in the Schedule of Assessments ([Table 1](#) and [Table 2](#)). Blood samples to evaluate ADAs will be collected at Screening to assess study eligibility and at the Early Termination (ET) visit, if applicable. ADA and CIC will be routinely monitored during the treatment period and throughout the open-label extension phase and safety follow up, as indicated in the Schedule of Assessments. Finally, ADA and CIC samples will also be collected and analyses will be performed and prioritized if any clinical evidence of progression of IgAN disease and/or relevant safety findings. Patients who are confirmed positive for IgG/IgM/IgA ADA at baseline will be excluded from study treatment. In addition, patients who develop de novo ADAs will be discontinued from study drug but will be followed until EOS visit and during safety follow up. These patients will also be monitored until ADA levels return to baseline.

Exploratory analysis of anti-Gd-IgA1 antibody levels will be conducted; serum samples for these analyses will be drawn when CIC samples are collected.

Details regarding the processing, shipping, and analysis of the samples will be provided in the Laboratory Manual.

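### On the latest OLE schedule available, ADA sampling leaves a 24-week, 6-dose interval (Weeks 48 to 72), twice the treatment-period maximum, for a stopping rule that depends on real-time sampling

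*Protocol*

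**What the plan says.** Section 1.5 describes a theoretical risk that antibodies to the GalNAc part of cemdisiran could cross-react with the autoantigen of IgA nephropathy. It judges that "The risk of developing these cross-reactive antibodies is likely low" and lists as mitigation "real time monitoring for development of de novo IgG/IgM/IgA ADAs after dosing with cemdisiran". Section 6.7.5.1 turns this into a rule: "patients who develop de novo ADAs will be discontinued from study drug but will be followed until EOS visit and during safety follow up". It also fixes when samples are drawn: "Blood samples for ADA and CIC testing must be collected before study drug administration". Section 6.7 places ADA among the safety assessments: "ECG findings and laboratory tests, including assessment of IgG/IgM/IgA ADA and CIC".

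On dosing, Section 3.1 states "The first study drug administration of the OLE will be administered at Week 36", then every 4 weeks. On visits it states "Patients will return to the study center at Week 40 and every 8 weeks thereafter during the OLE", with optional home visits in between (Weeks 44, 52, 60, 68 and 76).

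The ADA rows available are those of Amendment 1. Table 1 marks Screening, Day 1 and Weeks 4, 12, 24 and 32. It also marks Week 36, which the Amendment 1 rationale reserves for patients who do not continue into the OLE. Table 2 marks Weeks 48, 72 and 84 in the OLE, then safety follow-up.

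The Amendment 2 rationale says relevant OLE safety assessments should match those at first treatment, because ex-placebo patients meet cemdisiran for the first time there. Its log adds 4-weekly clinical laboratory and pregnancy tests from Week 36 to Week 64. The log as available lists no change to OLE ADA sampling.

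**The concern.** A rule that stops drug on confirmed ADA protects patients only as promptly as samples are drawn. In the initial protocol version ADA was collected descriptively, with no stopping rule, and its OLE row also reads Weeks 48, 72 and 84. Amendment 1 introduced the rule at a Health Authority's request, but its log adds ADA draws only at Screening, Week 36 and safety follow-up. None falls within OLE dosing. The OLE sampling thus appears to predate the rule it now has to serve.

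At stake is how many doses a patient with silent de novo ADA may receive before the rule can take effect. This concerns safety monitoring in the extension, not efficacy inference.

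**Working it through.** The protocol states no figure for sampling intervals, so the check is a count from the schedules.

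**Inputs**
- ADA is drawn predose (Section 6.7.5.1).
- Treatment-period doses: Day 1, then every 4 weeks to Week 32. Section 6.7.4 confirms a Week 32 dose: it times ECGs "in relation to the Day 1 and Week 32 cemdisiran or placebo doses".
- OLE doses: every 4 weeks from Week 36 (Section 3.1).
- ADA draws: Amendment 1 Table 1 (Day 1, Weeks 4, 12, 24, 32) and Table 2 (Weeks 48, 72, 84).

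Reading check on Table 2: the urinalysis row in the same table falls at Weeks 36, 40, 48, 56, 64, 72, 80 and 84, the expected center-visit pattern, so the columns are read correctly.

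**Counting rule.** Between a sample at week a and the next at week b, count doses at weeks d with a ≤ d < b, because both samples are predose.

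| Interval | Weeks | Doses |
|---|---|---|
| Treatment: Day 1 to 4 | 4 | 1 |
| Treatment: 4 to 12 | 8 | 2 |
| Treatment: 12 to 24 | 12 | 3 |
| Treatment: 24 to 32 | 8 | 2 |
| OLE, ex-placebo: first dose (36) to 48 | 12 | 3 (36, 40, 44) |
| OLE, ex-cemdisiran: 32 to 48 | 16 | 4 (32, 36, 40, 44) |
| OLE, all: 48 to 72 | 24 | 6 (48, 52, 56, 60, 64, 68) |
| OLE, all: 72 to 84 | 12 | at most 3 (72, 76, 80) |

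**Results**
- The longest treatment-period interval is 12 weeks and 3 doses. The longest OLE interval is 24 weeks and 6 doses, twice as long on both counts (24/12 = 2, 6/3 = 2).
- Doses before the first post-exposure sample: 3 for ex-placebo patients, 1 for patients first exposed on Day 1.
- Samples in the first 24 weeks after first exposure: ex-placebo 1 (Week 48, within Weeks 36 to 60); first exposed on Day 1, 3 (Weeks 4, 12, 24).

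**With samples added at Weeks 40 and 60**
- Ex-placebo doses between samples: 1 before Week 40, then 2 (to 48), 3 (to 60), 3 (to 72). Cumulative doses at sampling are 1, 3, 6 and 9. The first three match Weeks 4, 12 and 24 of the treatment period (1, 3, 6).
- Ex-cemdisiran: Week 32 to 40 is 8 weeks and 2 doses (32, 36), then 2, 3 and 3 as above.
- No interval exceeds 12 weeks or 3 doses in either group.

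No assumption on the timing of ADA onset enters these counts.

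**The case against.** **The governing table is not visible.** The available OLE schedule is Amendment 1's, and the current text refers to a schedule that cannot be read here. This stands. A reader might infer that the current protocol certainly contains the gap. The documents do not support that: the Amendment 2 log as available lists no OLE ADA change, which makes an unchanged row likely but not established.

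**Table 5 lists ADA under clinical laboratory assessments, so the added 4-weekly tests may already include it.** The ambiguity is real, but the reading is weak. ADA has its own schedule row. Table 5 lists pregnancy testing too, yet Amendment 2 named pregnancy tests separately when adding visits. A Table 5 item with its own row is therefore not carried in by the laboratory additions.

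**The Amendment 2 aim.** A reader might infer that the ADA row contradicts the stated aim of matching first-exposure assessments. That goes too far: the aim covers relevant assessments, its examples are laboratory and pregnancy tests, and ADA is not named. Section 6.7 makes ADA a natural candidate, no more.

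**The 3-dose lead-in is no worse than the treatment-period maximum.** Correct: 12 weeks and 3 doses equals the Week 12 to 24 interval. That is why the Week 48 to 72 interval is the main point and the lead-in secondary. Ex-cemdisiran patients also enter the long interval after scheduled samples at Weeks 4, 12, 24, 32 and 48.

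**Other safeguards exist, and no harm is shown.** Section 6.7.5.1 provides ADA sampling prompted by disease progression or safety findings, plus an early-termination sample. The DMC reviews unblinded ADA data (Section 3.7). In the Phase 1/2 study the one ADA-positive cemdisiran-treated volunteer was transiently positive, with no PK or PD impact (Section 1.2). These points limit severity. But prompted sampling needs a clinical trigger and the DMC sees only what was drawn, so neither finds silent ADA between scheduled samples.

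**Conclusion.** The point holds as an inexpensive improvement of low severity. On the latest OLE schedule available, all OLE patients have a 24-week, 6-dose interval without scheduled ADA sampling, against a 12-week, 3-dose maximum in the treatment period. In addition, at most about 10 ex-placebo patients (the placebo allocation, if all enter the optional OLE) receive 3 doses before their first post-exposure sample instead of 1. The stopping rule can therefore act late on silent de novo ADA.

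This rests on two assumptions: that the Amendment 2 ADA row is unchanged, and that dosing and sampling run on schedule. Confidence is medium because of the former.

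A reader might also infer that the sparse sampling has put patients at demonstrated risk, or that it weakens the trial's efficacy result. Neither follows. The documents give no ADA onset data from which to estimate harm, and the primary endpoint at Week 32 precedes the OLE.

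**What to change.** Check the ADA row in the current (Amendment 2) Table 2. Unless it already does so, add predose ADA samples at Week 40 and Week 60 and keep Weeks 48, 72 and 84. Both weeks already carry a laboratory draw under Amendment 2. Week 40 is a study center visit, and Week 60 can be drawn at home, which Section 6.7.5 allows for laboratory samples. A Week 36 predose sample is not needed for this purpose, since Week 32 is already sampled. A short statement that the 4-weekly laboratory tests do not include ADA would remove the Table 5 ambiguity.

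The cost is a schedule-table change and two extra tubes and assays per OLE patient: at most about 2 × 30 = 60 in total, with no extra visits. Limiting the additions to ex-placebo patients would need about 2 × 10 = 20, but would leave the 24-week interval for ex-cemdisiran patients.

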#### **6.7.5.2. Pregnancy Testing**

A pregnancy test will be performed for females of child-bearing potential. A serum pregnancy test will be performed at Screening and urine pregnancy tests will be performed thereafter per the Schedule of Assessments and any time pregnancy is suspected. The results of the pregnancy test must be known before study drug administration. Patients who are pregnant are not eligible for study participation. Any woman with a positive pregnancy test during the study will be discontinued from study drug but will continue to be followed for safety. Patients determined to be pregnant while on study will be followed until the pregnancy outcome is known (see Section [6.7.6.7](#) for follow-up instructions).

#### **6.7.5.3. Additional Liver Function Assessments**

Additional laboratory assessments will be performed in patients who experience any liver function test (LFT) abnormalities. Following the occurrence of elevated liver transaminases or other LFT abnormalities per central laboratory, all assessments in [Table 6](#) will be performed one time, as well as hematology, serum chemistry, LFT, and coagulation assessments from [Table 5](#), and other assessments or evaluations per Investigator discretion, as appropriate.

**Table 6: Hepatic Assessments in Patients Who Experience Elevated Transaminases**

Extended Hepatic Panel	
Herpes Simplex Virus 1 and 2 antibody IgM, IgG	HHV-6
Cytomegalovirus antibodies, IgM, IgG	HBs Ag, HBc antibody IgM and IgG
Anti-nuclear antibodies	Epstein-Barr Virus antibodies, IgM and IgG
Anti-smooth muscle antibodies	Anti-mitochondrial antibodies
HCV antibody	HAV antibody IgM
HCV RNA PCR – qualitative and quantitative	HEV antibody IgM
Herpes Zoster Virus IgM, IgG	
Imaging	
Abdominal ultrasound with Doppler flow (or CT or MRI) including right upper quadrant	
Focused Medical and Travel History	
Use of any potentially hepatotoxic concomitant medications, including over the counter medications and herbal remedies	Alcohol consumption
Other potentially hepatotoxic agents including any work-related exposures	Recent travels to areas where hepatitis A or E is endemic

Abbreviations: CT=computed tomography; HAV=hepatitis A virus; HBc=hepatitis B core; HBsAg=hepatitis B virus surface antigen; HCV=hepatitis C virus; HEV=hepatitis E virus; HHV-6=human herpesvirus 6; IgG=immunoglobulin G antibody; IgM=immunoglobulin M antibody; MRI=magnetic resonance imagery; PCR=polymerase chain reaction; RNA=ribonucleic acid.

Note:

- All assessments will be measured in central laboratory. The full panel of assessments should only be performed once; individual assessments may be repeated, as needed.

## 6.7.6. Adverse Events

### 6.7.6.1. Definitions

#### Adverse Event

According to the International Council on Harmonisation (ICH) E2A guideline Definitions and Standards for Expedited Reporting, and 21 CFR 312.32, investigational new drug (IND) Safety Reporting, an AE is any untoward medical occurrence in a patient or clinical investigational subject administered a medicinal product and which does not necessarily have a causal relationship with this treatment.

#### Serious Adverse Event

An SAE is any untoward medical occurrence that at any dose:

- Results in death

- Is life-threatening (an event which places the patient at immediate risk of death from the event as it occurred. It does not include an event that had it occurred in a more severe form might have caused death)
- Requires in-patient hospitalization or prolongation of existing hospitalization
- Results in persistent or significant disability or incapacity
- Is a congenital anomaly or birth defect
- Is an important medical event that may not be immediately life-threatening or result in death or hospitalization but may jeopardize the patient and may require intervention to prevent one of the other outcomes listed in the definition above (eg, events include allergic bronchospasm requiring intensive treatment in an emergency room or at home, blood dyscrasias, convulsions, or the development of drug dependency or abuse).

### Adverse Events of Clinical Interest

Based on the biological target and the available nonclinical and clinical data, AEs of Clinical Interest (AECI) for this study are:

- Severe infections as judged by the investigator
- ALT or AST  $>3\times$ ULN
- Severe or serious injection site reactions (ISRs); ISRs that are associated with a recall phenomenon (reaction at the site of a prior injection with subsequent injections), or those that lead to temporary dose interruption or permanent discontinuation of cemdisiran.

An ISR is defined as a local reaction at or near the site of injection. “At or near” the injection site includes reactions at the injection site, adjacent to the injection site, or a reaction which may shift slightly away from the injection site due to gravity (eg, as may occur with swelling or hematoma). A systemic reaction which includes the injection site (eg, generalized urticaria, other distinct entities or conditions like lymphadenopathy that may be near the injection site) is not considered an ISR.

For information on recording and reporting of AECIs, see Section 6.7.6.2 and Section 6.7.6.3 , respectively.

## Adverse Event Severity

Adverse events are to be graded according to the categories detailed below:

Mild: Mild; asymptomatic or mild symptoms; clinical or diagnostic observations only; intervention not indicated.

Moderate: Moderate; minimal, local or noninvasive intervention indicated; limiting age appropriate instrumental activities of daily living (eg, preparing meals, shopping for groceries or clothes, using the telephone, managing money).

Severe: Severe or medically significant but not immediately life-threatening; hospitalization or prolongation of hospitalization indicated; disabling; limiting self-care activities of daily living (ie, bathing, dressing and undressing, feeding self, using the toilet, taking medications, and not bedridden); OR life-threatening consequences; urgent intervention indicated; OR death related to an adverse event.

Changes in severity should be documented in the medical record to allow assessment of the duration of the event at each level of severity. Adverse events characterized as intermittent require documentation of the start and stop of each incidence. When changes in the severity of an AE occur more frequently than once a day, the maximum severity for the experience that day should be noted. If the severity category changes over a number of days, then those changes should be recorded separately (with distinct onset dates).

AE severity and seriousness are assessed independently. ‘Severity’ characterizes the intensity of an AE. ‘Serious’ is a regulatory definition and serves as a guide to the Sponsor for defining regulatory reporting obligations (see definition for SAE).

## Relationship of the Adverse Event to Study Drug

The relationship of each AE to study drug should be evaluated by the Investigator by a “yes” or “no” response to the question: “Is there a reasonable possibility that the event may have been caused by the study drug?”

### 6.7.6.2. Eliciting and Recording Adverse Events

#### Eliciting Adverse Events

The patient and legal guardian, if applicable, should be asked about medically relevant changes in the patient’s health since the last visit. The patient and legal guardian, if applicable, should also be asked if the patient has been hospitalized, had any accidents, used any new medications, or changed concomitant medication routines (both prescription and over-the-counter). In addition to patient observations, AEs will be documented from any clinically relevant laboratory findings, physical examination findings, ECG changes, or other findings that are relevant to patient safety.

